## 9. TRAINING PLAN

### 9.1. Training Plan for Research Device/Product

Training will be provided to study staff on the use of device system(s), as needed. Study staff that will be operating the device(s) during subject procedures may be required to receive additional training above that is required by other study staff. The Sponsor will provide instructions for use of the device and, as necessary, subsequent training, at the Sponsor's discretion or upon request by the site.

### 9.2. Training Plan for Protocol

Study staff will be trained on the study protocol and study procedures, including completion of Informed Consent Forms (ICFs), Case Report Forms (CRFs), and other study documentation.

Training will also be provided to ensure appropriate storage and handling of images and data. All study staff will be required to be trained on Good Clinical Practice (GCP) guidelines per ISO 14155: 2011.

A record of all formal training attendance and date conducted will be stored in the Site Regulatory Binder and provided to the Sponsor for inclusion in the Sponsor's Clinical History File (CHF).

### 9.3. Reader Training

All study staff assessing images for this study will be qualified radiologists at the investigational site(s), and reads will be performed according to the standard of care at the investigational site. All readers will be trained on the study protocol and on recording of data on CRFs prior to reading images. Determinations made by site radiologists based on DBT and FFDM images collected in this study may be included in the subject's regular medical record.

## 10. DATA ANALYSIS AND STATISTICS

### 10.1. Statistical Analysis Methods

#### 10.1.1. Sample Size Justification

The projected sample size is determined by the need to accrue at least 120 cancer cases and 250 non-cancer cases for the overall GE Healthcare SenoClaire® - GE Breast Tomosynthesis (DBT) development program. To achieve these overall accrual targets, the data from this study will be pooled with data from other studies (e.g. ADAPT-SCR and ADAPT-BX).

In this study, for an enrollment of 200 subjects recommended for breast biopsy, it is assumed, based on the GE-190-003 experience, approximately 33% are expected to have a proven cancer

and approximately 33% will have a benign lesion. So, at least 66 cancer cases and 66 non-cancer cases are expected to be accrued in this study. Up to 200 subjects referred for breast biopsy (enrollment ceiling per site will be 120 subjects) will be enrolled from up to two (2) centers located in the US until approximately 70 histopathology-confirmed cancers have been accrued. Enrollment will be managed to ensure equitable accrual of subjects across sites, if applicable.

Based on the GE-190-001 experience, for an enrollment of 250 subjects having screening mammography, about 185 (75%) will complete the study with a normal 1-year follow-up. Approximately 2% are expected to have a proven cancer either at screening or during follow-up, which will provide an estimated 6 cancer cases; expected to be accrued in the ADAPT-SCR protocol.

In the ADAPT-BX study, for a target enrollment of 275 subjects recommended for breast biopsy, it is assumed that, based on the GE-190-003 experience, approximately 33% are expected to have a proven cancer and approximately 33% will have a benign lesion. So, at least 90 cancer cases and 90 non-cancer cases are expected from the ADAPT-BX accrual.

Thus, in the combined ADAPT-SCR and ADAPT-BX protocols, it is expected that about 90 cancer cases and 250 non-cancer cases will be accrued, in which cancer cases were predominantly flagged using FFDM. To reduce the bias from the FFDM screening exam, cancer cases initially flagged using DBT will be accrued from this protocol, until at least 120 eligible cancer cases are accrued between the three protocols.

The data from this study will be pooled with data from the ADAPT-SCR and ADAPT-BX protocols. If necessary, data from other sources also may be included to achieve the required number of cancer and non-cancer cases. The accrued DBT and FFDM images will be used in a blinded image evaluation to analyze the diagnostic performance of SenoClaire® - GE Breast Tomosynthesis (DBT) compared to FFDM through receiver operating characteristic (ROC) analysis, sensitivity, specificity, recall rate, and other analyses.

No statistical analyses are included as part of this study. A descriptive summary will be provided for data collected in this study.

### **10.1.2. Study Populations**

The *Efficacy Population* will consist of those subjects meeting the study inclusion/exclusion criteria with no protocol violations judged to affect the ability to evaluate the subject whose DBT and FFDM images are diagnostically evaluable, and whose mammography images are available for the independent blinded evaluation regardless of the image quality. Non-available images will include:

- those lost due to corrupted media or inability of site to transport to image review center;
- subjects where no images are acquired.

The Sponsor will make any decisions regarding whether any subjects or any individual values belonging to a subject will be excluded from the evaluations when a protocol violation is

considered to have a negative impact on the scientific aspects and interpretation of the study results. The reason(s) for any exclusion(s) will be documented in the study report.

The *Safety Population* will include all subjects enrolled into the study.

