### 6.1. Type of Research Study

#### 6.1.1. Study Type

This study (ADAPT-Enrich) is an open-label, multi-center, within-subject crossover, prospective, clinical research study, collecting images and associated data from bi-lateral two-view DBT and FFDM exams conducted with GE systems. Study subjects will be initially asymptomatic adult women  $\geq 30$  years of age presenting for breast biopsy based on screening DBT plus standard of care diagnostic work-up.

The data from this study will be pooled with data from other subjects who will have been recruited under other GEHC protocols (including ADAPT-SCR and ADAPT-BX), for analysis described in a separate protocol (ADAPT-BIE). Figure 1 depicts the study design and procedures.

Figure 1: Study Design and Procedures

\*Images may be collected from FFDM and/or DBT performed on GE equipment prior to enrollment, if acquired within 30 days of each other.

\*\* If rebiopsy is not recommended or if histopathology remains discordant with imaging findings after rebiopsy, the subject will be withdrawn from the study.

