## 7.4. Procedures for Enrollment

All subjects must satisfy all the inclusion criteria and none of the exclusion criteria defined in the protocol. Subjects must sign and date the informed consent form prior to completing protocol specific procedures. The Investigator may discuss with the Sponsor any subject who does not strictly meet the inclusion/exclusion criteria but who is thought to be otherwise appropriate for the study; if the Sponsor and Investigator agree that inclusion of the subject would not affect the scientific or ethical aspects of the study, the Sponsor may provide a written exception for the subject. In this case, the details of the exception will be recorded on the Case Report Form (CRF). A subject will be considered enrolled when determined eligible and informed consent is signed, whether or not the subject undergoes study procedures.

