## 8. PROCEDURES FOR RESEARCH STUDY

Table 1: Study Schedule of Events for Study Subjects

Variables	Pre – Study Imaging	Study Imaging	Post- Study imaging
Informed Consent	X		
Entry Criteria	X		
Demographic Information a	X		
Review relevant Medical/Surgical History	X		
DBT Imaging	X		
Collection of two-view FFDM Imaging b	X	X	
Repeat of DBT or FFDM Imaging c		X	
Safety Assessments (AE, SAE, device malfunctions) d		X	
Image assessment by site radiologist			X
Histopathology			X

DBT = Digital Breast Tomosynthesis; FFDM = Full field digital mammography; AE = adverse event; SAE = serious adverse event;

a: Including age, menopausal status. b: FFDM imaging may be acquired at either time point.

c: Only if prior two-view screening and/or diagnostic images are not available or were not obtained on a GE system. d: Device-related AEs and SAEs reported.

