### 8.2. Digital Breast Tomosynthesis (DBT) and Full Field Digital Mammography (FFDM) Examinations

Prior screening DBT and screening/diagnostic FFDM images will be collected from each subject's medical record. If prior screening and/or diagnostic images/views are not available or were not collected with GE equipment, a subject will undergo study-specific DBT and/or FFDM imaging, as needed. Study-specific imaging may include bilateral 2-view (CC/MLO) FFDM and/or DBT (as needed) performed using GE systems available at the site and according to the site's standard procedures.

Two-view DBT and two-view FFDM image acquisition (both CC and MLO views) on GE equipment shall be performed within 30 days of each other, regardless if FFDM or DBT was performed before or after the patient agreed to participate in the study. Subjects requiring study-specific imaging will undergo the following procedures:

- Enter a changing room to prepare for their mammogram;
- Each subject of child-bearing potential shall wear a lead apron or have equivalent shielding during the DBT and/or FFDM procedures;
- Undergo DBT and/or FFDM procedure(s);
- Will be monitored for AEs and SAEs from study-specific DBT and FFDM and will be recorded in the source document and CRF. Device malfunctions shall be sent to the Sponsor as per Section 12.5 Management of Device Complaints.

All scanning should be performed within the standard range of scan parameters, as per the manufacturer-provided operator's manual(s) for GE FFDM and DBT devices. The scan operator should conduct DBT and FFDM exams according to the standard clinical practice at the site with consideration for:

- Subjects with large breasts, because perspiration under the breast can cause the skin to soften, and become paper-thin;
- Any existing condition that may cause unusual discomfort or tearing of the skin, which could include telling the subject the importance of correct positioning. The subject should be positioned carefully to avoid any discomfort to abnormalities such as warts, scarring, or skin which is not intact;
- Warmth of the breast support surface, which can be warm to the touch, as it contains electronic components that generate heat;
- Positioning the breast properly in FFDM and DBT in the CC position, where it is essential that the breast is lifted away from the chest wall and gently pulled forward, in order to visualize the maximum amount of breast tissue.

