#### **10.1.4. Adverse Events**

Adverse events will be reported from the time the subject enters the imaging suite for study procedures until the time the subject leaves the imaging suite after the study procedure. Device-related AEs and SAEs reported by subjects within 30 days of imaging (only those reported by subjects will be considered, and no separate 30-day follow-up is planned), and device malfunctions occurring in the safety population will be summarized with subject counts overall and by modality (DBT and FFDM). Additionally, individual subject listings will be provided to detail all AE/SAE information collected.

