## **15. DATA AND QUALITY MANAGEMENT**

### **15.1. Management of Data**

Images acquired during imaging (DBT and FFDM) examinations will be stored on an internal or external disk system for preliminary assessment, before permanent archiving.

The digital technology used by the devices in this study provides the ability to transfer acquired images between workstations, and to store them on hard disk. However, the hospital should utilize devices that are intended or approved as archiving devices for permanent storage of images.

Electronic image data (scan files) and associated data will be collected from subjects enrolled in this study and labeled with de-identified subject identification designation (SID) that will not contain any identifiable personal information. Images acquired by device procedures in this study will be handled by approved third-party contract research organizations (CROs).

FFDM and DBT images in this study will be collected from participating subjects in electronic format, which contains information about technical characteristics of the scan session. The Sponsor may extract and analyze electronic image data to determine technical information about the subject's scan session, including radiation dose information and other factors determined by the Sponsor. Applicable data extracted from electronic image files and calculated values based on such image data may be extracted and summarized by the Sponsor at an authorized engineering facility separate from the clinical site for the purposes of this study.

During this study, data and images from clinically indicated mammography (DBT and FFDM) occurring prior to the beginning of the subject's participation (date of consent) in this study period may be collected and provided to the Sponsor for research purposes. In the event of AE or SAE occurrence or appearance of incidental findings that initiate clinical follow-up, information about other interventions, including any diagnostic imaging results, will be recorded in the CRF and source images and/or other associated data may be provided to the Sponsor as part of this research study.

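### Does defining the Safety Population as all enrolled women spoil the adverse event summary, when only study-specific exams are actively monitored?

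*Combined protocol and SAP*

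**What the plan says.** Section 10.1.2 states that the Safety Population "will include all subjects enrolled into the study". Section 7.4 defines enrollment broadly: "A subject will be considered enrolled when determined eligible and informed consent is signed, whether or not the subject undergoes study procedures".

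Several places allow a woman to take part without a new exam. The Figure 1 note in Section 6.1.1 says "Images may be collected from FFDM and/or DBT performed on GE equipment prior to enrollment", subject to the 30-day window between modalities. Section 15.1 likewise lets the sponsor receive "images from clinically indicated mammography (DBT and FFDM) occurring prior to the beginning of" her participation. Note c to Table 1 in Section 8 limits repeat DBT or FFDM: "Only if prior two-view screening and/or diagnostic images are not available or were not obtained on a GE system".

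Monitoring follows the new exams. In Table 1 the row "Safety Assessments (AE, SAE, device malfunctions" is marked under Study Imaging only. Section 8.2 lists, for women who need study-specific imaging, "Will be monitored for AEs and SAEs from study-specific DBT and FFDM". Section 10.1.4 begins "Adverse events will be reported from the time the subject enters the imaging suite for study procedures" and closes that window when she leaves the suite. It then adds device-related events that women report themselves within 30 days of imaging, with no planned contact to ask for them.

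On output, Section 10.1.4 plans subject counts in the Safety Population, overall and by modality, plus individual listings. Section 10.1.1 says the study contains no statistical analyses and will be summarized descriptively.

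**The concern.** The population used for the safety summary can be larger than the set of women watched for events. A woman with eligible GE DBT and FFDM from before consent is in the Safety Population, yet she never enters the imaging suite for a study procedure. Her events appear only if she volunteers them or if they are otherwise recorded under Section 12.3.

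A count of events means little without the number of women in whom events could be seen. If a reader took all enrolled women as that number, a low count would look more reassuring than it should, and a count of zero most of all. Section 10.1.3 does not clearly close the gap. It summarizes women *imaged* by modality and image acquisition, but does not say whether prior clinical exams are included. If they are, nearly every woman is imaged in both modalities.

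**Working it through.** **The plan's own figure.** There is none to reproduce. The documents state no event rate, no safety N other than all enrolled, and no precision target for safety.

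**Inputs.** Maximum enrollment is 200 (Section 7.1). The number n with study-specific imaging is not given, so I assume n = 200, 150, 100, 50 and 20 (100% down to 10% of 200).

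**Step 1: do the planned counts change?** Study procedures require consent first (Section 7.4), so every monitored woman is enrolled and therefore in the Safety Population. No monitored event is lost, and self-reports from the other women are kept. The planned counts and listings are the same whatever n is.

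**Step 2: what would an unplanned percentage do?** Suppose m monitored women have an event and s other women report one. The rate among monitored women is m/n. A percentage over all enrolled is (m + s)/200. The understatement factor is

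(m/n) ÷ ((m + s)/200) = (200/n) × m/(m + s), which is at most 200/n.

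It equals 200/n only when s = 0. With zero events among n monitored women, the one-sided 95% upper bound on risk is 1 − 0.05^(1/n).

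| n monitored (assumed) | Largest factor, 200/n | 2 events over 200 enrolled | 2 events over n | Zero-event upper bound |
|---|---|---|---|---|
| 200 | 1.00 | 1.0% | 1.0% | 1.49% |
| 150 | 1.33 | 1.0% | 1.33% | 1.98% |
| 100 | 2.00 | 1.0% | 2.0% | 2.95% |
| 50 | 4.00 | 1.0% | 4.0% | 5.82% |
| 20 | 10.00 | 1.0% | 10.0% | 13.91% |

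One self-report from an unmonitored woman shows why these factors are limits. With n = 100, m = 2 and s = 1, the rates are 2/100 = 2.0% and 3/200 = 1.5%, a factor of 1.33 and not 2.

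**Step 3: can the monitored number be recovered?** The 30-day rule between DBT and FFDM (Sections 7.5 and 8.2) cannot be checked without exam dates, and the consent form is dated. Comparing the two separates exams before consent from those after it. A clinical exam done after consent would still need the site's record to tell it from a study-specific one. The number is therefore obtainable when the tables are made, although Section 10.1.4 does not ask for it.

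**The case for a change.** The strongest case for a change is that exams without monitoring are part of the design, above all for DBT. Every woman must already have had screening DBT to be eligible. Table 1 marks DBT imaging before study imaging only, so a study DBT arises only as a repeat. FFDM may fall at either time. The number monitored for DBT could thus be well below enrollment and differ from the number for FFDM, while the safety endpoint in Section 5.3.3 is described by modality. Listings show the women with events; they do not count those watched without one. Adding the number would cost one figure overall and one per modality, and fixing it beforehand avoids choosing a denominator once events are known.

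All of this is correct as a reading of the text, and a careful analyst would print the monitored number beside the counts. What it does not show is an error in the plan. No percentage, bound or DBT-versus-FFDM safety comparison is planned for the wrong denominator to enter, and Section 10.1.4 discloses the narrow observation window alongside the counts it promises.

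The all-enrolled definition also has a purpose: it keeps self-reports and malfunctions that arise outside a monitored exam. Nor would sorting women into monitored and pre-consent-only settle everything. A woman with a pre-consent DBT and a study-specific FFDM who reports an event from the DBT fits neither group, so events would have to be sorted by the exam concerned.

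**Conclusion.** No change to the plan is needed. The Safety Population is wider than the monitored set, and Section 10.1.4 leaves the monitored number unstated, but following the plan as written gives correct counts and complete listings. What is missing is table-layout detail that analysts can supply.

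The possible harm is confined to a percentage the plan does not contain, or to a reader who supplies the wrong denominator. Its size cannot be computed from the documents. It is nil if every woman has study-specific imaging and at most 200/n otherwise, assuming full enrollment of 200 and no counted events from unmonitored women. If the study report does give percentages, the number of women with a study-specific exam started, overall and per modality, is the natural denominator for events from those exams.

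The stakes are modest. The devices are commercially available and designated non-significant risk (Section 4.1), the foreseeable effects are bruising, discomfort and skin injury (Section 12.1), and success is judged on accrual alone (Section 10.4).

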#### **10.1.3. Subject Disposition and Characteristics**

Subjects enrolled, imaged, and withdrawn will be summarized overall and by site and imaging modality. Descriptive statistics and summaries will be provided for demographics, medical histories, image acquisition, lesions and findings.

Specific subgroups of interest include stratification by the following variables:

- Age;
- Menopausal status; and
- Breast density.

#### **10.1.4. Adverse Events**

Adverse events will be reported from the time the subject enters the imaging suite for study procedures until the time the subject leaves the imaging suite after the study procedure. Device-related AEs and SAEs reported by subjects within 30 days of imaging (only those reported by subjects will be considered, and no separate 30-day follow-up is planned), and device malfunctions occurring in the safety population will be summarized with subject counts overall and by modality (DBT and FFDM). Additionally, individual subject listings will be provided to detail all AE/SAE information collected.

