#### 5.3.3. Safety endpoints

Device-related adverse events (AEs), serious adverse events (SAEs), and device malfunctions by overall occurrence and imaging modality (DBT and FFDM) that occur during the study will be collected. No other clinical safety assessments will be performed.

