## 6.2. Study Timeframe

The study is expected to begin in late 2015, and last for approximately two years (24 months), or until the target subject population is enrolled or the Sponsor otherwise indicates in writing that enrollment should be terminated. The end of the study shall be defined as the date when the last subject undergoes biopsy procedures and concordance is established, if applicable. Subject participation will be from the point of enrollment until truth determination of cancer status. The Investigator shall not begin the study until the applicable EC/IRB and necessary regulatory authority approvals, when required, have been obtained.

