## 12.3. Management of Adverse Event Reporting

Any adverse events will be recorded in the subjects study record and the Adverse Event Case Report Form. The following information should be obtained:

- Description of Event

- Date of onset and resolution
- Intensity (mild, moderate, severe)
  - **Mild:** Symptom(s) barely noticeable to the subject or does not make the subject uncomfortable. The AE does not influence performance or functioning. Prescription drugs are not ordinarily needed for relief of symptom(s).
  - **Moderate:** Symptom(s) of a sufficient severity to make the subject uncomfortable. Performance of daily activities is influenced. Treatment of symptom(s) may be needed.
  - **Severe:** Symptom(s) of a sufficient severity to cause the subject severe discomfort. Treatment for symptom(s) may be given.
- Serious (yes/no)
- Relationship to device (unrelated, possibly related, probably related)
  - **Unrelated:** The adverse event is reasonably expected to be related to (or caused by) a concurrent illness, effect of another device/drug or other cause, and is unlikely related to the investigational product
  - **Possibly related:** The adverse event is reasonably expected to be related to the investigational product, and an alternative etiology is equally or less likely compared to the potential relationship to investigational product
  - **Probably related:** There is a strong relationship to investigational product, or recurs on re-challenge, and another etiology is unlikely, or there is no other reasonable medical explanation for the event.
- Treatment given and/or action taken (procedure stopped, withdrawn from study, no action)
- Anticipated (yes/no)

Adverse events will be reported to the local EC/IRB per their policy.

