## **12.4. Management of Serious Adverse Event and Unanticipated Adverse Device Effect Reporting**

All SAEs and or UADEs will be documented as above and reported in writing to the Sponsor within 72 hours of knowledge of the event. The Investigator shall submit the Adverse Event Case Report Form and GEHC\_GQP\_10.07.005\_F002 Site Notification and Assessment of Serious and Unexpected Adverse Events (DOC0910335) with redacted supporting documentation to SAE mailbox.

If the event resulted in the death of a subject, the event shall also be reported via telephone to the Sponsor within 24 hours of knowledge of the event. SAEs will be reported to the local EC/IRB per their policy.

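### Read literally, Section 10.1.4 counts only subject-reported device-related events, which is narrower than the Section 5.3.3 safety endpoint and the staff monitoring in Section 8.2

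*Combined protocol and SAP*

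**What the plan says.** Section 10.1.4 contains four statements that bear on this point.

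- AEs are reported "from the time the subject enters the imaging suite for study procedures until the time the subject leaves the imaging suite".
- Device-related AEs and SAEs reported by subjects within 30 days of imaging, together with device malfunctions, are summarized as subject counts, overall and by modality.
- A parenthesis limits those AEs and SAEs: "only those reported by subjects will be considered, and no separate 30-day follow-up is planned".
- In addition, "individual subject listings will be provided to detail all AE/SAE information collected".

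Section 5.3.3 defines the safety endpoint as device-related AEs, SAEs and device malfunctions "by overall occurrence and imaging modality (DBT and FFDM) that occur during the study will be collected". It does not say who must report them.

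Section 8.2 requires women who have study-specific imaging to be monitored for AEs and SAEs, with the results entered in the source document and CRF. Table 1 schedules safety assessment at study imaging only. Section 12.3 states: "Any adverse events will be recorded in the subjects study record and the Adverse Event Case Report Form". Section 12.4 requires SAEs and UADEs to be "reported in writing to the Sponsor within 72 hours of knowledge of the event".

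**The concern.** The counts in Section 10.1.4 are the only tabulation planned for the safety endpoint. If they admit only what the woman herself reports, the table measures something narrower than the endpoint it is meant to summarize.

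The protocol itself expects staff to see events. Section 12.1 lists bruising, abrasions and skin tears, all of which are visible to an examiner. Section 8.7.1 refers to pain, discomfort or unstable vital signs noticed by inspection or on monitoring equipment. Further contact is also likely. Exclusion criterion 2 bars procedures on either breast before study-related imaging, so biopsy comes after imaging, and Section 6.2 says: "Subject participation will be from the point of enrollment until truth determination of cancer status". Clinicians will often examine the imaged breast again while the woman is still a participant.

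What is at stake is agreement between the safety table and its own source records. A reader of the report could find an event in the listing that does not appear in the count, with no explanation. Section 15.1 says the image data are intended for a US regulatory submission, so that mismatch is worth avoiding.

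**Working it through.** The plan gives no AE rate and no expected safety count, so there is no figure to reproduce. The check is a comparison of the text.

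**1. Which rule governs each step**

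| Step | Section | Limited to subject reports? | Window |
|---|---|---|---|
| Endpoint definition | 5.3.3 | No | During the study |
| Monitoring and recording | 8.2 | No, staff monitor | Study-specific imaging |
| Recording on the AE form | 12.3 | No | Not stated |
| SAE/UADE notification | 12.4 | No, runs from knowledge of the event | 72 hours from knowledge |
| AE reporting | 10.1.4, first sentence | No | Suite entry to suite exit |
| Summary counts | 10.1.4, second sentence | **Yes** | 30 days from imaging |
| Listings | 10.1.4, last sentence | No | All information collected |

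The summary counts are the only step restricted by who reports the event.

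**2. Following one event through the rules**

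Suppose staff note a device-related skin tear within 30 days of study-specific imaging and the woman does not mention it.

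- It belongs on the AE form (12.3).
- It goes to the Sponsor if it is an SAE or UADE (12.4).
- It appears in the individual listing (10.1.4).
- It does not enter the subject counts (10.1.4, parenthesis).

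The last step applies even if the tear is seen in the imaging suite. The sentence that defines the counts makes no exception for events found by the monitoring in Section 8.2.

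**3. Direction and size**

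Let d be the number of women with a device-related event known to the site within 30 days. Let s be the number of those women whose events were all noted only by staff. The table then shows d − s. Since 0 ≤ s ≤ d, the shortfall s lies between 0 and d and cannot be negative. The same holds within each modality.

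Neither d nor s can be filled in. The documents give no event rate, no split by reporter and no imaging-to-biopsy interval. The number of women exposed to study-specific imaging is not fixed either. Up to 200 may be enrolled, but under Section 8.2 and note c of Table 1 that imaging is done only where suitable GE images are not already available. So 200 is an upper limit.

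**4. The windows**

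Three windows are in use: the imaging suite and 30 days (both in 10.1.4), and the whole study (5.3.3). Changing the parenthesis alone would leave the suite-only sentence in conflict with the 30-day one.

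**The case against.** The best counter-argument is that the parenthesis should be read as a whole. Paired with the statement that no separate 30-day follow-up is planned, it may describe only passive surveillance: once the woman has left the suite, unsolicited reports are accepted and nobody contacts her. Nothing in the documents states an intention to discard what staff observe, and Section 8.4 does not mention adverse events at biopsy. This is a plausible account of what was meant. It does not remove the point, because the sentence as written is an explicit rule, and a programmer applying it would leave staff-only events out.

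A reader might also infer three stronger things that the documents do not support.

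- **That such events are lost from the report.** They are not. They remain on the AE form and in the Section 10.1.4 listings; only the counts omit them.
- **That Section 10.1.4 contradicts Sections 12.3 and 12.4.** Those sections govern recording and notification, not tabulation. The real tension is with the endpoint in Section 5.3.3 and the monitoring in Section 8.2.
- **That Section 6.2 closes AE intake before day 30.** Participation may end before then, but nothing in Section 6.2 stops a later report from being accepted, and Section 10.1.4 counts subject reports up to day 30 regardless.

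It is also fair to say that the consequences are limited. This is an accrual study with no hypothesis test (5.1) and no statistical success criterion (10.4), the devices are commercially available, and the safety summary is descriptive.

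**Conclusion.** The point stands as a mismatch between the endpoint and its summary. Read literally, the Section 10.1.4 counts leave out device-related events noted only by staff, although Section 5.3.3 sets no such limit and Section 8.2 requires staff to look for them. The effect is on the summary counts alone and runs in one direction, downward. Its size lies between zero and the full count and cannot be narrowed from the documents; any specific percentage would be invented.

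The conclusion assumes that the sentence is applied as written. If passive surveillance was all that was meant, no event would be left out in practice, but the wording should still say so. No efficacy result, sample size or study conclusion changes. The correction is worth making because the table and its listing should agree and the remedy is small.

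**What to change.** In Section 10.1.4, replace the parenthesis and the restriction to subject reports. State that the summary covers all device-related AEs and SAEs that the site becomes aware of by any route (subject report, staff observation or medical record) within 30 days of study-specific imaging, and that no additional visit or active follow-up is required.

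In the same edit, reconcile the windows. The suite-entry-to-exit sentence in Section 10.1.4 could be recast as the period of staff monitoring at study-specific imaging, with the 30 days as the window for the counts. The study-long wording in Section 5.3.3 should then refer to that window. Section 6.2 needs no change.

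The cost is wording in Sections 10.1.4 and 5.3.3. No visit is added. The one downside is that the reported event count may be slightly higher.
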